3.9 Adherence

3.9.1 Adherence to Trial Medication

The planned daily dose is 1 pill per day. Low and standard doses are dispensed in separate bottles. Adherence to trial medication will be computed overall (across both low and standard doses).

Trial medication adherence over the run-in period will be presented as below:

 Adherence to active run-in treatment specified as the number of pills taken compared to the planned number of pills for the period, expressed in percentage. The planned number of pills for the period will be determined as the expected number of days of treatment between the Period 1 first dose date and Period 1 last dose date. The number of pills taken is determined as the difference between number of pills dispensed and the number of pills returned. For participants with missing pill-return data, 100% adherence will be assumed for the associated period.

Trial medication adherence over the randomized period (from randomization to Week 12) will be assessed

using the following parameters:

- Denominator: Planned number of pills for the period is defined as the number of days between the scheduled first and last treatment intake. The medication log CRF will be used to determine the number of expected days by computing the number of days between the start and stop dates for each record and summing across all records reported for each participant. Note, if there is a gap between the stop and start records for sequential medication logs, gap days will be assigned an expected count of 0.
- Numerator: The number of pills taken is determined as the difference between number of pills dispensed and the number of pills returned. For participants with missing pill-return data, it will be assumed that the number of pills taken equals the minimum of the number of pills dispensed for that period and the number of days between the logged start and stop date for the corresponding trial medication log.

Adherence to trial medication will be calculated as numerator \div denominator and expressed in percentage. Adherence is confirmed if $\ge 80\%$ and $\le 120\%$.

Additional details surrounding the calculations of numbers of pills dispensed and adherence will be described within a specifications document.

3.9.2 Adherence to Home BP Measurement

As per Section 8.2.1 in the protocol, adherence to home BP monitoring schedule will be assessed at the randomization visit. In the week before randomization (week -1), at least 6 measures (e.g., \geq 2 sets of triplicate measures, \geq 3 sets of duplicate measures) are required including at least 1 morning and 1 evening, each with \geq 2 measures. Morning is defined as any measure in the AM and evening as any measure in the PM. Morning and evening do not have to be same day.

Following randomization, a minimally valid half-day of BP measurements is defined as one that has either:

- ≥1 BP values in the morning (earlier than 12:00 hours), or
- ≥ 1 BP values in the evening (12:00 hours or later).

Study protocol Section 10.2.8 instructs that in the week before the Randomization, Week 6, and Week 12 trial visits, BP measurements should be taken on the 4 days immediately prior to the day of the on-site trial visit. In other weeks, measurements should be performed on a single day.

Adherence to home BP measurement will be evaluated by looking at the number of minimally valid half-days and will be summarized by counting the number of minimally valid AM and PM periods of BP measurements per week of follow-up, by treatment group and overall.

3.9.3 Protocol Deviations

Over a blind review meeting, before database lock, the different protocol deviations will be classified as minor or major and categorized by type (e.g. non-compliance to treatment, prohibited medication etc.) by the clinical team. The number of major protocol deviations will be summarized by type of deviations.

Major protocol deviation categories include, but are not limited to:

- Randomized even though ineligible.
- Received the wrong treatment.
- Non-adherence to study treatment (adherence < 80% or > 120%), for reasons known to be unrelated

to tolerability or efficacy e.g. participant moved overseas.

- Interruption to study treatment as a result of supply chain issues in which protocol-specified procedures were not followed.
- Insufficient valid home BP measurements for home blood pressure calculation at one or more of: baseline, Week 6 Follow-up Visit 1, Week 12 Follow-up Visit 2.
- Up-titration at Week 6 Follow-up Visit 1 was not performed for reasons other than those specified in the protocol.
- Other

A summary table will present the tabulations by major protocol deviation on the Safety Set. All protocol deviations (recorded or programmed) will be listed.

- 2) Randomized Set excluding participants with IMP interruptions for supply-related reasons
- 3) Complete cases with Clinic BP Substitution: Participants with missing Baseline, Week 6, or Week 12 Home BP assessments with Clinic BP recorded will have their clinic measured value substituted for the missing Home BP assessment at the respective visit. Any participants with missing Baseline or Week 12 assessments without an in-clinic assessment at the designated visit will be excluded.
- 4) Per Protocol Analysis Set: Excluding any participants with an intercurrent event or major protocol deviation.

3.10.1.1 Secondary Estimands

The population for the secondary estimands includes adults (aged \geq 18 years) with hypertension. Participants in the trial will complete a 4-week single-blind active run-in on the experimental product GMRx2-Dose2 and then be randomized to treatment. The variables of interest are listed in Section 2.4.1.2.

Hypothesis testing is not planned for secondary endpoints and, therefore, the results of the planned analyses are considered exploratory. Statistical analyses for continuous secondary endpoints will be performed on Complete Cases only. Statistical analyses for binary secondary endpoints will be performed on the Randomized Set, where participants with missing endpoints values will be assumed to have not achieved the endpoint (i.e., missing data will be singly imputed as "failure").

Table 3-2 Estimands

Estimand Label	Treatment	Population	Population-level summary	Analysis	Handling of Intercurrent
Primary Analysis	GMRx2 vs dual combinations at week 12	Adults with hypertension	Difference in change in home SBP, for GMRx2 vs each dual combination separately Analysis will be performed using Mixed Model with Repeated Measures (MMRM) with Multiple Imputation	Randomized Set	Treatment policy strategy with intercurrent events only used as part of missing data imputation strategy
Primary Estimand, Sensitivity Analysis – Week 12 only	GMRx2 vs dual combinations at week 12	Adults with hypertension	Difference in change in home SBP, for GMRx2 vs each dual combination separately Analysis will be performed using Mixed Model with Repeated Measures (MMRM) with Multiple Imputation, Week 12 results only	Randomized Set	Treatment policy strategy with intercurrent events only used as part of missing data imputation strategy
Primary Estimand, Sensitivity Analysis – Adjusted Analysis	GMRx2 vs dual combinations at week 12	Adults with hypertension	Difference in change in home SBP, for GMRx2 vs each dual combination separately Analysis will be performed using Mixed Model with Repeated Measures (MMRM) with Multiple Imputation, adjusted for covariates	Randomized Set	Treatment policy strategy with intercurrent events only used as part of missing data imputation strategy

Estimand Label	Treatment	Population	Population-level summary	Analysis	Handling of Intercurrent
	Comparison			Population	events
Primary Estimand,	GMRx2 vs dual	Adults with	Difference in change in home SBP, for	Randomized Set	Treatment policy strategy
Sensitivity	combinations	hypertension	GMRx2 vs each dual combination separately		with intercurrent events only
Analysis –	at week 12				used as part of missing data
Subgroup Analysis			Analysis will be performed using Mixed		imputation strategy
			Model with Repeated Measures (MMRM)		
			with Multiple Imputation, with interaction		
			terms for specified subgroups		
Primary Estimand,	GMRx2 vs dual	Adults with	Difference in change in home SBP, for	Full Analysis Set	Treatment policy strategy
Supplemental	combinations	hypertension	GMRx2 vs each dual combination separately		with intercurrent events only
Analysis	at week 12				used as part of missing data
			Analysis will be performed using MMRM		imputation strategy
			with Multiple Imputation		
Primary Estimand,	GMRx2 vs dual	Adults with	Difference in change in home SBP, for	Randomized Set	Treatment policy strategy
Supplemental	combinations	hypertension	GMRx2 vs each dual combination separately	excluding	with intercurrent events only
Analysis	at week 12			participants with	used as part of missing data
			Analysis will be performed using MIMRM		imputation strategy,
			with Multiple Imputation	interruptions for	excluding participants with
				supply-related	IMP Interruptions due to
				reasons	supply-related reasons
Primary Estimand,	GMRx2 vs dual	Adults with	Difference in change in home SBP, for	Randomized Set,	I reatment policy strategy
Supplemental	combinations	hypertension	GMRX2 vs each dual combination separately	Complete Cases	with substitution of missing
Analysis	at week 12			with Clinic BP	home BP assessments with
			Analysis will be performed using MIMRM	Substitution	clinic BP assessment values
			WITH CIINIC BP Substitution		(participants missing both
					nome and clinic BP values will
					be excluded from analysis)

Estimand Label	Treatment	Population	Population-level summary	Analysis Population	Handling of Intercurrent
Primary Estimand, Supplemental Analysis	GMRx2 vs dual combinations at week 12	Adults with hypertension	Difference in change in home SBP, for GMRx2 vs each dual combination separately Analysis will be performed using MMRM	Per Protocol Set	All participants with intercurrent events and major protocol deviations excluded from analysis
Secondary Estimands, Continuous Endpoints	GMRx2 vs dual combinations at specified timepoints	Adults with hypertension	Continuous Endpoints: Analysis will be performed using MMRM, Summary variable will be LS Means and LS Mean Difference	Randomized Set	Treatment Policy Strategy for intercurrent events with results reported. Complete cases only with no imputation for missing data.
Secondary Estimands, Binary Endpoints	GMRx2 vs dual combinations at specified timepoints	Adults with hypertension	Dichotomous Endpoints: Analysis will be performed using GEE, Summary variable will be Odds Ratios, Risk Difference, and corresponding confidence intervals (CIs)	Randomized Set	Treatment Policy Strategy for intercurrent events with results reported. Missing data will be imputed as "failure".

3.10.2 Primary Efficacy Analysis

3.10.2.1 Definition – Home BP

Home seated systolic and diastolic BP measurements will be averaged as described in Table 3-3 and the following endpoints will be derived:

- Average home SBP during the 7 days prior to Randomization visit, Week 6 FU1 visit and Week 12 FU2 visit
- Average home DBP during the 7 days prior to Randomization visit, Week 6 FU1 visit and Week 12 FU2 visit
- Average trough (i.e. measurement taken before morning dose) home SBP during the 7 days prior to Randomization visit, Week 6 FU1 visit and Week 12 FU2 visit

Note that trough will be assumed to be any BP measure taken in the morning, as participants are instructed to perform the BP measurement prior to taking their daily medication and to take that medication in the morning.

Measure	Rules
Randomization, week 6 and week 12 home BP	 Defined as the home BP in the week before randomization, FU visit 1 (scheduled at Week 6) and FU visit 2 (scheduled at Week 12), respectively. FU visits 1 and 2 may not occur exactly at 6 and 12 weeks, respectively.
Individual BP measurement	 Each BP measurement must consist of valid SBP and DBP values. (i.e., SBP>60 mmHg and <250 mmHg and DBP>40mmHg and <150mmHg). If valid SBP and DBP are not recorded, the entire measure will be discarded. Recommended home BP measurements were for 4 consecutive days immediately prior to the trial visits (i.e. Week -1, Week 5, Week 11) and on a single set day of the participant's preference in other weeks.
Grouping of measurements into sessions	 Individual BP measurements must be grouped into 5-minute "sessions". To group individual BP measurements into sessions, the start of a 5-minute period is at the time of the first measurement with all BP measurements in those 5 minutes being assigned to the single session. A new session starts at the first BP measure encountered after the completion of an existing session. If more than two measures are captured in a session then, as with three measures, the second and third measures with be flagged for use. The first and any measures after the third are ignored. In the case of fewer than three BP measures in a session, all measures will be flagged for use.
Selection of a single session per half-day period	 Each day is divided into two half-days – AM and PM. If more than one session occurs in one period e.g., two sessions in the AM period of a given day, one session only will be selected for use using two prioritisation steps:

Table 3-3 Definitions of Home Blood Pressure Derivations

	 Sessions containing three or more BP measures will be prioritised over those with two. Those with only one BP measure will be used as a last resort. If the first step does not uniquely select one session for the period, the earliest session of those selected in the first step will be used.
Calculation of averages	 To calculate an average, perform a simple, unweighted mean of the flagged BP measurements in the selected sessions for the period of interest. At Randomization: A minimum of 6 measures (e.g. ≥2 sets of triplicate measures or ≥3 sets of duplicate measures) are expected, including at least 1 morning and 1 evening, each with ≥2 measures per protocol-specified eligibility criteria. Post-Randomization: At least 4 consecutive calendar days (8 measurement sessions, 24 BP readings) were recommended. Calculations: For all timepoints, calculations of averages will be performed if there is at least 1 valid BP measurement. The home BP values for the purpose of Baseline, FU visit 1 Week 6 and FU visit 2 Week 12 are averages (as defined above) across up to 7 calendar days immediately preceding each in-clinic visit. Each of the up to 2 selected sessions per day (1 morning and 1 evening) may be included in the calculation. Days with no valid measures reported will be excluded from the calculation (i.e., only days with SBP measurements recorded will be included in average).

In addition, for descriptive plots of SBP and DBP measurements post-randomization, weekly average BP will be computed where Week is defined in relation to the randomization date with Week 1 initiating on Day 1, the first treatment with randomized trial medication:

Week = (date of BP measurement - date of first dose of randomized treatment)/7Week is rounded up to the nearest integer. Averages will otherwise be calculated in the same manner as described in Table 3-3.

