3.5 General Methods

All data listings that contain an evaluation date will contain a relative study day. Two relative study days will be defined: Period 1 Relative Day (P1 Rel Day) and Post-Randomization Relative Day (PR Rel Day). For Period 1 Relative Day, pre-treatment and on-treatment study days are numbered relative to the day of the first dose of single-blind study treatment which is designated as P1 Day 1. The preceding day is P1 Day -1, the day before that is P1 Day -2, etc. Post-Randomization Relative Day will be numbered relative to the day of the first dose of the randomized medication which is designated as PR Day 1.

The planned treatment group for all participants in Period 1 is GMRx2. In Period 2, the planned treatment group is randomly assigned to be:

- 1. Triple TAI (GMRx2) : telmisartan (T) 20 mg/amlodipine (A) 2.5 mg/indapamide (I) 1.25 mg.
- 2. Dual TA: telmisartan 20 mg/amlodipine 2.5 mg.
- 3. Dual TI: telmisartan 20 mg/indapamide 1.25 mg.
- 4. Dual AI: amlodipine 2.5 mg/indapamide 1.25 mg.

Up-titration is planned to occur prior to Period 3, resulting in planned treatment at increased dose levels; however, the up-titration may not occur for reasons as specified in the protocol (Section 8.4.2). Therefore, treatments in period 3 include:

Treatment Group	Period 2: Treatment	Period 3: With Up-	Period 3: No Up-Titration
	(Planned)	titration (Planned)	
Triple – TAI	telmisartan (T) 20 mg/	telmisartan 40 mg/	same as in Period 2
	amlodipine (A) 2.5 mg/	amlodipine 5 mg/	
	indapamide (I) 1.25 mg.	indapamide 2.5 mg	
	(GMRx2 Dose2)	(GMRx2 Dose3)	
Dual – TA	telmisartan 20 mg/	telmisartan 40 mg/	same as in Period 2
	amlodipine 2.5 mg	amlodipine 5 mg	
Dual – TI	telmisartan 20 mg/	telmisartan 40 mg/	same as in Period 2
	indapamide 1.25 mg	indapamide 2.5 mg	
Dual – Al	amlodipine 2.5 mg/	amlodipine 5 mg/	same as in Period 2
	indapamide 1.25 mg	indapamide 2.5 mg	

Table 3-1 Planned Treatment Assignments Period 2 and Period 3

All output will be incorporated into Microsoft Word or Adobe Acrobat PDF files, sorted and labelled according to the ICH recommendations, and formatted to the appropriate page size(s).

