3.10.2.9 Descriptive figures

The following graphical displays are planned:

- Plot of the LS Mean home SBP with 95% CI derived from the MMRM for the primary analysis will be presented.
- Results from the tipping point analysis will be presented graphically.
- Forest plots of the LS Means, 95%Cl and p-values for determining heterogeneity by subgroup will be presented.
- Descriptive scatter plots to display the average weekly SBP post-randomization, where Week 1 begins at first treatment post-randomization, Week 2 begins at Day 8 of treatment post-randomization, etc.
- Descriptive scatter plots to display the change in average weekly SBP from randomization through the Randomization Period. Randomization will be defined as the 7 calendar days prior to the Randomization clinic visit (Table 3-3). The Randomization Period will begin on the first day of randomized treatment and will extend until the earliest of: Week 12 visit, End of Study visit, or 14

weeks of post-randomized BP home measurements.

• Descriptive scatter plots to display the change in average weekly SBP from end of Phase 2/FU1 visit through Period 3. End of Phase 2/FU1 visit will be defined as the 7 calendar days prior to the FU1 Week 6 clinic visit (Table 3-3). Period 3 will begin on the first day of treatment following FU1 Week 6 clinic visit and will extend until the earliest of: Week 12 visit, End of Study visit, or 7 weeks of Period 3 BP home measurements.

Scatter plots may be presented for the treatment groups overall as well as by subgroups, as appropriate. Similar plots may be presented for home DBP, as appropriate.

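### The SAP's week formula for the descriptive home BP plots is one day off from the SAP's own definition of Week 1 and Week 2

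*SAP*

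**What the plan says.** Four statements in the SAP bear on this.

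- **Day numbering (SAP 3.5).** Post-randomization days are counted "relative to the day of the first dose of the randomized medication which is designated as PR Day 1". There is therefore no Day 0 on this scale.
- **Week definition (SAP 3.10.2.1, text after Table 3-3).** The plots are to have "Week 1 initiating on Day 1, the first treatment with randomized trial medication".
- **Week formula (same place).** Week is ("date of BP measurement - date of first dose of randomized treatment") divided by 7, with the result rounded up to a whole number.
- **Week definition again (SAP 3.10.2.9).** Weekly SBP is displayed "where Week 1 begins at first treatment post-randomization, Week 2 begins at Day 8 of treatment post-randomization".

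The formula's scope is stated: "for descriptive plots of SBP and DBP measurements post-randomization, weekly average BP will be computed". The home BP values used as Baseline, Week 6 and Week 12 come from a different rule in Table 3-3, an average "across up to 7 calendar days immediately preceding each in-clinic visit".

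**The concern.** A formula that subtracts two dates returns 0 on the first-dose day, whereas the SAP numbers that day 1. Unless one day is added back before dividing, each week boundary falls a day late. The first-dose day lands in a Week 0, and each later bin takes in the first day of the next week.

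At stake is the correctness and reproducibility of the planned weekly displays. One programmer could follow the formula and another the sentence that introduces it. Both would comply with the SAP, yet their figures would differ. A Week 0 point holding only the first-dose day could also be mistaken for the baseline, which SAP 3.5.2 and Table 3-3 define differently.

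**Working it through.** **Inputs.** Day 1 is the first randomized dose day (SAP 3.5), so date difference = Day − 1. The formula and its rounding rule come from SAP 3.10.2.1. The target boundaries are Week 1 from Day 1 (SAP 3.10.2.1) and Week 2 from Day 8 (SAP 3.10.2.9).

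**Formula as written:** Week = ceiling((Day − 1)/7). **With one day added:** Week = ceiling((Day − 1 + 1)/7) = ceiling(Day/7).

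| Day | Difference | As written | With +1 | SAP's week definition |
|---|---|---|---|---|
| 1 | 0 | 0/7 → 0 | 1/7 → 1 | 1 |
| 2 | 1 | 1/7 → 1 | 2/7 → 1 | 1 |
| 7 | 6 | 6/7 → 1 | 7/7 → 1 | 1 |
| 8 | 7 | 7/7 → 1 | 8/7 → 2 | 2 |
| 9 | 8 | 8/7 → 2 | 9/7 → 2 | 2 |
| 43 | 42 | 42/7 → 6 | 43/7 → 7 | 7 |
| 78 | 77 | 77/7 → 11 | 78/7 → 12 | 12 |
| 84 | 83 | 83/7 → 12 | 84/7 → 12 | 12 |

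The SAP states the Week 1 and Week 2 boundaries outright. The later entries in the last column continue them in seven-day steps.

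**Count over Days 1–84.** The formula disagrees with the definition on Days 1, 8, 15, 22, 29, 36, 43, 50, 57, 64, 71 and 78. That is 12 of 84 days, or 12/84 = 14.3%, each one week too early. As written, Week 0 holds one day, Weeks 1–11 hold seven days each, and Week 12 holds six (1 + 77 + 6 = 84). With one day added, Weeks 1–12 hold seven days each and every day agrees with the definition.

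**Other rounding rules.** Neither alternative rescues the formula. Rounding down gives Day 1 → 0 and Day 8 → 1, and rounding to the nearest integer gives the same two results. Rounding down and then adding 1 works: Day 1 → 1 and Day 8 → 2.

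**Effect on one participant.** Outside the pre-visit weeks, home BP is ideally measured on one set day per week (Protocol 10.2.8). Suppose that day is the weekday of the first randomized dose. Each single-day week's only readings then fall on a misassigned day, and that point is plotted one week early. In the weeks before the Week 6 and Week 12 visits, readings are scheduled on four consecutive days. At most one of those four can be the first-dose weekday, so the average is not displaced as a whole.

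**The case against.** **Scope.** The formula serves descriptive plots only and treats every arm alike, so it cannot bias a comparison. That stands. A reader might infer from the labels Week 6 and Week 12 that the primary endpoint is affected, but Table 3-3 ties those values to the days before each clinic visit and does not use this formula.

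**Up-titration.** A reader might infer that readings on the higher dose are plotted in Week 6. The documents do not support that as a general statement, because two day scales are in play. In the visit schedule, randomization is Day 0 and the Week 6 visit is Day 42. If the first randomized dose is taken on the randomization visit day, the day after a Day 42 visit has a difference of 43, and 43/7 = 6.14 rounds up to Week 7. It falls in Week 6 only if the first dose is taken the day after randomization (42/7 = 6), or if Day 42 is read on the SAP 3.5 scale. Even then, the morning reading is taken before that day's dose. The visit window of ±7 days also moves the dose change across weekly bins under either formula, and SAP 3.10.2.9 plans a separate plot referenced to the Week 6 visit.

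**Size for an individual.** A reader might also infer that some participants have every weekly point a week early. The four-day pre-visit weeks rule that out. The documents give no distribution of set days, so the share of participants affected is unknown. It would be about 1 in 7 only if set days were spread evenly over the week.

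**Intent.** The formula might be meant for date-times, or meant to keep a pre-dose Day 1 reading out of Week 1. The text says date, and it places Day 1 in Week 1. With date-times and a roughly constant dosing time, a pre-dose morning reading on Day 8 would still generally fall in Week 1, against SAP 3.10.2.9. The question about pre-dose Day 1 readings is fair, however: the SAP should settle it, since adding one day places them in Week 1.

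**Conclusion.** The formula is wrong as written. It contradicts the week definition that introduces it and the one in SAP 3.10.2.9. It misplaces 12 of Days 1–84 (14.3% of days) by one week and creates an undefined Week 0. The result rests only on the SAP's day numbering and on reading the formula as a difference of calendar dates.

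The consequence is minor. The error is common to all arms and confined to the descriptive weekly home BP displays. The Week 6 and Week 12 home BP endpoints, and the tests on them, do not depend on it. At participant level it can move a point by a full week only in single-day weeks, and only when the set day is the weekday of the first dose.

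**What to change.** In SAP 3.10.2.1, replace the formula with:

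Week = ceiling((date of BP measurement − date of first randomized dose + 1)/7), equivalently floor(difference/7) + 1.

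Add a sentence saying whether readings taken on Day 1 before the first randomized dose count in Week 1. If they are to be left out, say so explicitly and do not rely on the formula to exclude them.

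The cost is one corrected line, one added sentence and the matching line of plot code. No new data are needed, and no endpoint, test or trial procedure changes.
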